2. STUDY PROCEDURES

a. Procedures

Patients from our endocrinology practice meeting our inclusion criteria will be consented into the study. They will be randomized into 1 of 2 treatment arms (Anastrozole 1 mg qday or Letrozole 2.5mg qday). Labs (gonadotropins, androgens, estrogens, growth factors, lipid profile) will be done every 6 months, bone age annually, and DEXA scans every 2 years.

We will see the patients annually until near final height (< 2 cm growth velocity per year), re-consenting in those over 18 years old. We will perform physical exams, obtain

anthropometric data, and repeat the above blood tests at least once off medication and perform imaging studies as warranted.

Beginning with this March 2016 renewal, we will no longer randomize to A vs L but use only A, continuing to collect observational data. **Procedure Risks**

We will be using the standard doses for the two drugs used. We will be monitoring with every 6 month physical exams and laboratory evaluation for possible side effects. At the discretion of the investigator, the medication may be reduced or discontinued, specifically if growth velocity falls below normal. **Use of Deception in the Study**

No deception will be used. Use of Audio and Video Recordings

No audio or video recording will occur. Alternative Procedures or Courses of Treatment

There are no alternatives to the above treatment. The only alternative would be to not start on the medication. Growth hormone is a theoretical option but is not standard of care for patients meeting these inclusion criteria. No standard treatment will be withheld. Will it be possible to continue the more (most) appropriate therapy for the participant(s) after the conclusion of the study?

Yes

g. Study Endpoint(s)

Our end point is final height which is defined as less than 2 cm of growth per year. We anticipate that all patients will reach this end point. **BACKGROUND**

a. Past Experimental and/or Clinical Findings

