Randomization to Letrozole vs. Anastrozole in Short Pubertal Males

NCT02137538

June 24, 2021

[name], Principal Investigator [name], Principal Investigator Stanford University Stanford, California 94305

Statistical Methods

Baseline auxologic and hormonal measures were summarized by treatment arm. Laboratory measures over time were presented as means with standard deviation, with key measures (total testosterone, estradiol, IGF-1) additionally displayed as boxplots by arm. Growth velocity (cm/year), height (cm), bone age (months), predicted adult height (cm), and DEXA z-scores over time were similarly visualized. Adverse events were listed by arm, and spinal film was assessed qualitatively.

To include all patients in an intent-to-treat approach, mixed effects linear regression was used to model each outcome as a function of treatment arm, indicators for follow-up timepoints, and their interaction for assessing effect modification of annual change by arm. Within-patient correlation was accounted for by a random effect. Estimated change since baseline with 95% confidence intervals were presented by arm if effect modification was deemed significant at the 0.05 alpha level and as an overall effect otherwise. All analyses were performed in the R statistical computing framework, version 4.0¹.

¹ R Core Team (2020). R: A language and environment for statistical computing. R Foundation for Statistical Computing, Vienna, Austria. URL https://www.R-project.org/

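### The SAP model gives each arm its own baseline mean, so for randomised boys the modelled drug contrasts are in effect unadjusted change-score differences: unbiased, but less precise than the collected baseline values could allow

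*SAP*

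**What the plan says.** The SAP, under Statistical Methods, will "model each outcome as a function of treatment arm, indicators for follow-up timepoints, and their interaction". On correlation it adds: "Within-patient correlation was accounted for by a random effect". The reporting rule is: "Estimated change since baseline with 95% confidence intervals were presented by arm if effect modification was deemed significant at the 0.05 alpha level". If the interaction is not significant, one change pooled over both arms is shown.

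The only other use of baseline in the SAP is descriptive: "Baseline auxologic and hormonal measures were summarized by treatment arm". It names no baseline covariate and no constraint that the arms share a baseline mean.

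On who is analysed, the SAP says: "To include all patients in an intent-to-treat approach, mixed effects linear regression was used". Protocol section 2a says of the boys: "They will be randomized into 1 of 2 treatment arms". The same section later says: "Beginning with this March 2016 renewal, we will no longer randomize to A vs L but use only A, continuing to collect observational data".

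**The concern.** A change since baseline can come out of this model only if baseline is the reference timepoint and one of the modelled responses. The arm coefficient is then a free difference in baseline means, and each arm-by-timepoint coefficient is a between-arm difference in change.

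For boys who were randomised, the true baseline means are equal. The free term spends information on a quantity known to be zero, and the noise in the observed baseline difference passes in full into the contrast. A baseline-adjusted analysis would subtract only the part of that difference that predicts follow-up.

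The comparison of the two drugs is the stated purpose of the study (protocol section 1), and the hormone profile is part of it. Because the interaction test decides whether results are shown by arm at all, a loss of power here does more than widen an interval: it can take the drug comparison out of the report. Randomisation has ended, so the randomised comparison cannot gain more boys.

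**Working it through.** **No plan figure to reproduce.** The protocol plans 120 boys (section 6a) but gives no effect size, SD, power or allocation ratio, so that number cannot be derived. The SAP gives no within-boy correlation.

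**Inputs.** From the documents: the model terms, one random effect, 0.05 for the interaction test, 120 planned. Assumed: 1:1 allocation (60 per arm), a random intercept, a two-sided test, and rho between 0.3 and 0.9. The number randomised before March 2016 is not given.

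**Step 1: what the interaction estimates.** I fitted the SAP model by generalised least squares to simulated data with baseline and three follow-ups. With complete data, the last-visit interaction equalled the raw difference in mean change (for example -0.0158 and -0.0158 at rho 0.5). With 30% of follow-up values missing at random the two were close but not identical (0.126 and 0.107 at rho 0.5).

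**Step 2: variance, equal SDs, complete data.** Per unit variance, the contrast at one visit has variance proportional to

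- SAP model: 1 + 1 - 2 rho = 2(1 - rho)
- common baseline or own-baseline covariate: 1 - rho^2

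The ratio is (1 - rho^2) / [2(1 - rho)] = (1 + rho)/2, so the saving is (1 - rho)/2. The least-squares calculation gave the same ratios.

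| rho | SAP | adjusted | saving | SAP interval wider by | boys for the same precision | saving, 30% of follow-up missing |
|---|---|---|---|---|---|---|
| 0.3 | 1.40 | 0.91 | 35% | 24.0% | 78 of 120 | 29% |
| 0.5 | 1.00 | 0.75 | 25% | 15.5% | 90 of 120 | 20% |
| 0.7 | 0.60 | 0.51 | 15% | 8.5% | 102 of 120 | 12% |
| 0.9 | 0.20 | 0.19 | 5% | 2.6% | 114 of 120 | 4% |

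**Step 3: power.** Suppose the SAP contrast at one visit had 80% power with 60 per arm. The adjusted power is Phi(2.80/sqrt(ratio) - 1.96). At rho 0.5 this is Phi(2.80/0.866 - 1.96), about 90%. At rho 0.3, 0.7 and 0.9 it is about 93.5%, 86% and 82%. The SAP does not say whether its test is joint over timepoints, so these figures illustrate the scale only.

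**Step 4: chance imbalance.** With equal SDs and an observed baseline difference d, the expected error of the SAP contrast given d is -(1 - rho)d. At rho 0.5 and d = 0.3 SD that is 0.5 x 0.3 = 0.15 SD, in the direction of regression to the mean. It averages to zero over randomisations.

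**Step 5: unequal SDs.** Let k be the follow-up SD divided by the baseline SD. The SAP variance is 1 + k^2 - 2 rho k; the adjusted variance is k^2(1 - rho^2). At rho 0.5:

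- k = 1: 1.00 against 0.75, saving 25%
- k = 1.5: 1.75 against 1.6875, saving 4%
- k = 2: 3.00 against 3.00, saving 0% (the regression slope rho k is then exactly 1)

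At rho 0.3 and k = 2 the variances are 3.80 and 3.64, a saving of 4%.

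**Step 6: does simply deleting the arm term work?** Not always. With a single random intercept and one follow-up, the implied slope is the covariance over the average variance. At rho 0.5 and k = 2 this is 1/2.5 = 0.4. The variance becomes 4 + 0.16 - 2(0.4)(1) = 3.36 against 3.00, which is 12% worse.

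**The case against.** The strongest reply is that nothing here is invalid. Under randomisation the SAP contrast is unbiased. Chance imbalance in one sample is what its interval is there to cover. That stands. A reader might infer from Step 4 that regression to the mean biases the drug comparison or inflates type I error; neither follows. A reader might also infer that baseline is thrown away, but subtracting it does use it, only with a slope that is usually not the best one.

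The size is uncertain in two directions that the documents cannot settle: rho and the SD ratio. It is tempting to say that the loss is largest for hormones and lipids. That needs modest visit-to-visit correlation and a stable spread on treatment, and neither is documented. Protocol section 7a lists raised testosterone as a risk of treatment, so the spread of that measure could change (an assumption). If height tracks strongly within a boy (also an assumption), the gain there is small. Averaging over visits could give larger savings, but the SAP specifies no such average.

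Nor is every drug comparison affected. Adverse events are listed and spine films read qualitatively, and no growth velocity before treatment is described that could serve as a baseline.

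Finally, the equal-baseline premise holds only for boys randomised before the March 2016 renewal. The SAP says it includes all patients and does not say how any later anastrozole-only boys are handled. If they are in the model, a free arm mean is defensible for them, and forcing a common baseline could introduce bias. That point stands and limits the remedy.

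**Conclusion.** The concern holds as a matter of efficiency. For modelled outcomes with a baseline value, the SAP's arm-by-timepoint terms are in effect unadjusted differences in change: exactly so with complete data and a random intercept, approximately so otherwise. Among randomised boys they are unbiased, but generally less precise than a baseline-adjusted contrast and more sensitive to chance imbalance.

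The likely cost runs from negligible to about a third of the variance over the range examined. The upper end needs low correlation, similar SDs at baseline and follow-up, and little missing follow-up; a follow-up SD well above baseline can remove it. The loss gains importance from the reporting rule, under which a missed interaction means that no estimate is shown by arm.

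**What to change.** First identify the boys randomised before the March 2016 renewal. In that set, for each outcome with a baseline value, add one of two analyses:

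- **Common-baseline (constrained longitudinal) model.** Keep timepoint and arm-by-follow-up terms, drop the arm main effect, and use an unstructured or otherwise time-varying covariance in place of a single random intercept. Step 6 shows why the covariance must change too. Boys who lack a baseline or a follow-up value stay in.
- **Own-baseline adjustment.** Take follow-up values as the response, with the outcome's own baseline interacted with timepoint. Boys who lack a baseline value or all follow-up drop out unless values are imputed.

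The two are not equivalent when data are incomplete, so name one in advance of the refit. The first sits better with the SAP's aim of keeping all patients. Do not impose a common baseline on boys who were not randomised. Report the between-arm difference with its confidence interval whether or not the interaction is significant.

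The SAP is dated June 2021 and written in the past tense, so show the refit beside the SAP's own model and label it as added later. No new data are needed. The cost is a small amount of extra analysis and a few more covariance or slope parameters to estimate.

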We will ask the patients about other studies they may be enrolled in although we do not anticipate that this will occur.

k. Payments to Participants

No payments

I. Costs to Participants

Clinic visits, drugs, and laboratory charges which are considered standard of care will be the patient's responsibility.

m. Planned Duration of the Study

We anticipate the average length of treatment to be 2-3 years. We will evaluate the patients every 6 months with laboratory evaluation with the same frequency. After treatment, follow-up visits will be scheduled annually until growth is completed, which will be on average an additional 3-4 years (6-7 years from start of treatment). Subjects will be re-consented upon reaching 18 years of age.

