We will be monitoring for arthralgia with the clinical history every 6 months. We will also collect laboratory data every six months: lipids, insulin levels, as well as estrogen and testosterone, gonadotropin and growth hormone levels. We will perform DEXA scans at baseline and two years into study to assess for decreases in bone density. Access to the labs/scans are all password protected.

d. Study Conclusion

The endpoint is final height. We will terminate when the growth rate has decreased to less than 2 cm per year. Since we will be monitoring clinical and performing physical exams every 6 months, if any of the side effects have been clinically significant, we will treat accordingly and/or terminate the use of the therapy.

e. Data Safety Monitoring Plan (DSMC)

i. Data and/or events subject to review

We will be monitoring, through laboratory evaluation, lipids, insulin sensitivity, gonadotropins, sex steroids, and growth hormone levels. We will monitor for changes in bone density through DEXA scans. Person(s) responsible for Data and Safety Monitoring

Protocol Director Frequency of DSMB meetings

All labs/scans will be monitored as soon as theyhave been received from the reference lab. Specific triggers or stopping rules

Physician's clinical assessment based on laboratory evaluation. DSMB Reporting

As needed

vi. Will the Protocol Director be the only monitoring entity? (Y/N)

Yes

vii. Will a board, committee, or safety monitor be responsible for study monitoring? (Y/N)

No

f. Risks to Special Populations

Short-term studies of aromatase inhibitors in this age group have not shown any significant risks, but there is a theoretical risk of issues with bone density, testicular function, and alterations to lipids/carbohydrate metabolism that is present. We will be monitoring for these risks during the course of the study. The direct benefit is increased ultimate height. We will be discussing these theoretical risks with the family in depth and will be obtaining assent from the subjects themselves. **BENEFITS**

Greater final height for the individual participant and possibly improved treatment options for future patients.

9. **PRIVACY AND CONFIDENTIALITY**

All participant information and specimens are handled in compliance with the Health Insurance Portability and Accountability Act (HIPAA) and privacy policies of Stanford University, Stanford Health Care, and Stanford Children's Health.

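### The SAP's only drug comparison is a multi-term arm-by-timepoint test of unstated form, and no single letrozole–anastrozole difference is sure to be reported

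*SAP*

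**What the plan says.** The SAP (Statistical Methods) states that "mixed effects linear regression was used to model each outcome as a function of treatment arm", together with "indicators for follow-up timepoints, and their interaction for assessing effect modification of annual change by arm". Of the correlation between visits it says only: "Within-patient correlation was accounted for by a random effect". Estimated changes from baseline, with confidence intervals, are shown separately by arm "if effect modification was deemed significant at the 0.05 alpha level and as an overall effect otherwise".

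The SAP does not list the timepoints in the model, does not say whether the interaction is tested jointly or by coefficient, and names no single contrast.

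The protocol supplies the schedule. Section 2a says "Labs (gonadotropins, androgens, estrogens, growth factors, lipid profile) will be done every 6 months", with bone age annually and DEXA every two years. Section 7c places DEXA at baseline and two years. Section 6m says "We anticipate the average length of treatment to be 2-3 years" and puts total follow-up at 6–7 years on average. Section 2g makes final height the endpoint, and section 1a makes comparing the two drugs the purpose of the study.

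**The concern.** The SAP describes its target as a difference in annual change, which sounds like one number per outcome. Its model uses categorical time, so the interaction is a set of visit-specific differences. A single 0.05 decision over such a set can mean two things with different properties. A joint test gives up power when the difference follows one simple pattern. A rule that any coefficient below 0.05 counts gives up error control.

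The result also decides what is reported. If it is not significant, the arms are pooled. If it is significant, a change is shown for each arm. Neither branch commits to the difference between the drugs with its own confidence interval, so the comparison the study was set up to make might not be estimated for some or all outcomes.

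**Working it through.** The documents give no power, effect size or SD, so there is no figure of theirs to reproduce. The check uses a benchmark.

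**Inputs**
- Alpha 0.05 (SAP); two-sided is assumed.
- K, the number of follow-up timepoints, from Protocol 2a and 6m. Labs every six months over 2–3 years give K = 4–6. Annual measures give K = 2–3 on treatment, and about 6–7 if annual visits to final height are modelled. DEXA with one follow-up gives K = 1. Because the SAP lists no timepoints, these are assumptions.
- The single random effect is read as a random intercept (assumption). In units of the residual variance, the covariance of the K differences in change is then proportional to V = I + J, where J is the matrix of ones. Each variance is 2 and each covariance 1, so the correlation is 1/2.
- Benchmark: one contrast with 80% power (assumption).

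**Joint test, all signal along one contrast**

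Non-centrality λ = (1.960 + 0.842)² = 7.85. Power is the probability that a non-central chi-square with K degrees of freedom and this λ exceeds the central 95% point. The sample multiplier is the λ needed for 80% power at K degrees of freedom, divided by 7.85.

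**Any coefficient below 0.05**

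For independent tests the error is 1 − 0.95^K. For equal correlation r it comes from 1,000,000 simulated draws.

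| K | Joint power | Sample multiplier | Any-visit error, r = 0.5 | r = 0.8 | Independent |
|---|---|---|---|---|---|
| 1 | 80% | 1.00 | 5% | 5% | 5% |
| 2 | 70.9% | 1.23 | 9.1% | 7.8% | 9.8% |
| 3 | 64.5% | 1.39 | 12.5% | 9.8% | 14.3% |
| 4 | 59.5% | 1.52 | 15.6% | 11.4% | 18.5% |
| 5 | 55.5% | 1.63 | 18.3% | 12.8% | 22.6% |
| 6 | 52.1% | 1.74 | 20.6% | 13.9% | 26.5% |
| 7 | 49.3% | 1.83 | 23.0% | 14.9% | 30.2% |

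**Dependence on the pattern of the difference**

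Scale the difference d at the last visit so that the last-visit contrast has 80% power: d/√2 = 2.802, so d² = 15.70. The joint test has λ = g′V⁻¹g with V⁻¹ = I − J/(K+1). The average over visits has variance 1 + 1/K.

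For K = 4:
- Constant difference: λ = 15.70 × 4/5 = 12.56, joint power 82%. The average contrast has z = 3.962/√1.25 = 3.54, power 94%.
- Linear divergence (¼, ½, ¾, 1 of d): λ = 15.70 × (1.875 − 6.25/5) = 9.81, joint power 71%. The average has z = 3.962 × 0.625/√1.25 = 2.21, power 60%.
- Last visit only: λ = 15.70 × (1 − 1/5) = 12.56, joint power 82%. The average has z = 3.962 × 0.25/√1.25 = 0.89, power 14%.

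The same joint calculation for other K, against 80% for the last-visit contrast:
- Constant or last-visit-only difference: 83% (K = 2), 83% (K = 3), 79% (K = 6).
- Linear divergence: 71% (K = 2), 70% (K = 3), 75% (K = 6).

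**The case against.** The best defence is that a joint arm-by-time test is a standard and valid test of whether change from baseline differs by arm. It holds error at 5% within an outcome and keeps sensitivity to patterns nobody foresaw. That stands, and the pattern results support it. No single contrast wins everywhere: at K = 4 the average beats the joint test for a constant difference (94% against 82%) but loses under linear divergence (60% against 71%) and badly for a last-visit-only difference (14% against 82%). The last-visit contrast gains clearly only under divergence (80% against 71%).

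A reader might infer four stronger things that the documents do not support:
- *That the joint test loses much of its power in general.* The loss in the first table requires the signal to lie along the chosen contrast, and the documents do not establish the pattern.
- *That the plan inflates false positives.* The any-visit rule is one possible reading and is not stated. The power loss and the error inflation are alternatives and do not occur together.
- *That every outcome is affected.* The protocol says "We will perform DEXA scans at baseline and two years into study". With one follow-up, K = 1 and neither problem arises.
- *That long strings of late visits are certainly in the model.* The SAP refers to annual change and lists no timepoints. If only annual on-treatment timepoints were modelled, labs too would have K = 2–3.

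The defence does not answer the missing test rule, or the absence of a guaranteed estimate of the drug difference.

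**Conclusion.** The concern holds as a defect of specification and reporting. The SAP's only drug comparison is a multi-term interaction whose test is not defined, and its result determines whether the arms are separated or pooled. The cost depends on which reading was used:
- **Joint test:** valid error within an outcome. Where the signal follows one contrast, the loss from 80% is about 9–15 points at K = 2–3 and 20–28 points at K = 4–6. There is little or no loss against a last-visit contrast for a constant or last-visit-only difference.
- **Any coefficient:** error of about 9–23% for K = 2–7 at correlation 0.5, and about 8–15% at correlation 0.8.

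These sizes rest on the assumed K, correlation, two-sided testing and 80% benchmark. The missing test rule and the conditional reporting do not depend on those assumptions.

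**What to change.** For each outcome, report from the same model one named one-degree-of-freedom arm difference in change, with its 95% confidence interval, whatever the interaction p-value:
- Hormones and lipids: difference in mean on-treatment change over the scheduled visits.
- Bone age and predicted adult height: difference in change at one stated on-treatment timepoint, for example 24 months.
- Height: arm difference at near-final height, which keeps the protocol's endpoint in the inference, with 24 months as secondary.
- DEXA with one follow-up: the interaction is already a single contrast, so report its estimate and interval.

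List the timepoints in each model, state whether the test used was joint or per coefficient, and keep the joint test as supportive. The SAP is dated June 2021 and written in the past tense, so any contrast added after it should be labelled post hoc.

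The cost is some SAP wording and one contrast statement per outcome, with no new data. The downside is real: a single contrast is less sensitive to patterns it does not target, such as a difference at one other visit or, for the average, a late divergence. The supportive joint test partly covers this.

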5. DRUGS, BIOLOGICS, REAGENTS, OR CHEMICALS USED IN THE STUDY

a. Investigational Drugs, Biologics, Reagents, or Chemicals

Investigational Product 1		
Name:	NA	
Dosage:	NA	
Administration Route:	NA	

b. Commercial Drugs, Biologics, Reagents, or Chemicals

Commercial Product 1		
Name:	Letrozole (no longer being used)	
Dosage:	2.5 mg	
Administration Route	Oral	
New and different use? (Y/N)	Yes	
Commercial Product 2		
Name:	Anastrozole	
Dosage:	1 mg	
Administration Route	Oral	
New and different use? (Y/N)	Yes	

6. **PARTICIPANT POPULATION**

a. Planned Enrollment

120; boys with short stature and/or growth hormone deficiency which may be congenital or acquired (post surgical or chemotherapy)

b. Age, Gender, and Ethnic Background

Males 10-17.99 years old, any ethnic background (identical to our clinical population) were recruited; those over 18 years old at f/u are reconsented,

c. Vulnerable Populations

The study is directed towards children because the purpose of the study is to evaluate growth. We will be monitoring for side effects closely.

d. Rationale for Exclusion of Certain Populations

All boys who fit under our inclusion criteria, regardless of ethnic background, will be included. Girls are excluded as aromatase inhibitor therapy will increase testosterone, causing untoward effects for girls.

e. Stanford Populations

None

f. Healthy Volunteers

None

g. Recruitment Details

The first person identifying patients for recruitment will be physicians in the Pediatric Endocrine Division at Lucile Packard. The protocol director will then continue the recruitment process in more detail.

h. Eligibility Criteria

i. Inclusion Criteria

Outpatient males with: Age 10-17.99 years; re-consented if over 18 years old at follow up Current height less than 5th percentile OR Predicted adult height (based on bone age) more than 10 cm below target height (mid parental height)

- Lab evidence of puberty: serum LH >0.3 IU/L and testosterone >15 ng/dl
- ii. Exclusion Criteria

Bone age xray more than 14 years FSH >20 IU/L

i. Screening Procedures

Pediatric endocrinologists will recruit all patients who qualify based on our inclusion criteria. Qualifying labs and bone age xray are usually obtained as part of routine clinical assessment of boys with short stature and/or delayed puberty, or would be obtained after enrollment and consent.

j. Participation in Multiple Protocols

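### If the SAP's single random effect is a patient random intercept, the 95% intervals for change in height and bone age are probably mis-sized: too wide early and too narrow late if boys' growth diverges

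*SAP*

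**What the plan says.** The SAP (Statistical Methods) models each outcome on treatment arm, "indicators for follow-up timepoints, and their interaction for assessing effect modification of annual change by arm". On correlation it has one sentence: "Within-patient correlation was accounted for by a random effect". It mentions no random slope, visit covariance, serial correlation or robust standard error. On reporting: "Estimated change since baseline with 95% confidence intervals were presented by arm if effect modification was deemed significant at the 0.05 alpha level", and otherwise as one overall effect. Height in cm and bone age in months are among the outcomes followed over time.

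The Protocol describes the population in section 6. Planned enrolment (6a) is "120; boys with short stature and/or growth hormone deficiency which may be congenital or acquired (post surgical or chemotherapy"; on age (6b), "Males 10-17.99 years old, any ethnic background (identical to our clinical population) were recruited". Eligibility (6h) narrows this by requiring "Lab evidence of puberty: serum LH >0.3 IU/L and testosterone >15 ng/dl" and excluding "Bone age xray more than 14 years". Bone age is taken annually (section 2), and treatment is expected to last 2-3 years on average with six-monthly evaluations (6m).

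**The concern.** A patient random intercept with constant residual variance implies one variance for the change from baseline, whichever visit is compared. That is a poor description of an outcome that accumulates. If some boys gain height or bone age faster than others, their curves separate, and the true variance of the change differs by visit. The fitted model replaces those variances by a single average.

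At stake is the SAP's main reported quantity, the estimated change with its 95% interval. The error is the same in relative terms whether the change is shown by arm or pooled. If spread widens, the last modelled visit looks more precisely estimated than it is. A secondary effect falls on the 0.05 interaction test, which decides between by-arm and overall reporting.

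The point is limited to height and bone age. It makes no claim about growth velocity, predicted adult height, DEXA z-scores or laboratory values.

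**Working it through.** The documents give no SD, interval width or power figure, so there is no stated figure to reproduce.

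**Assumed inputs.** Annual visits at 0-2 or 0-3 years; residual SD σ = 0.5 or 1.0 cm; between-boy SD of velocity s = 0.25 to 1.5 cm/yr; complete data.

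**Formulas, n boys.**
- True variance of change at year t: (2σ² + t²s²)/n if each boy keeps one fixed rate deviation; (2σ² + t·s²)/n if his yearly deviations are independent.
- Random-intercept variance, the same at every visit: the average of the true variance of the difference over all pairs of visits. Fixed deviations: (2σ² + 2s²)/n for 0-2 y, since (1+1+4)/3 = 2; (2σ² + 10s²/3)/n for 0-3 y, since (1+1+1+4+4+9)/6 = 10/3. Independent deviations: 4s²/3 and 5s²/3 replace these terms.
- SE ratio r = √(model variance / true variance); coverage = 2Φ(1.96r) − 1.

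**Worked case: σ = 0.5, s = 1.0, fixed deviations (variances times n).**
- 0-2 y: model 0.5 + 2 = 2.5. True 1.5 and 4.5 at years 1 and 2. r = 1.291 and 0.745; coverage 98.9% and 85.6%.
- 0-3 y: model 0.5 + 3.333 = 3.833. True 1.5, 4.5 and 9.5. r = 1.599, 0.923 and 0.635; coverage 99.8%, 93.0% and 78.7%.

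**Same inputs, independent yearly deviations, 0-3 y.** Model 0.5 + 1.667 = 2.167. True variance at year 3 is 3.5. r = 0.787; coverage 87.7%.

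**Last-visit coverage for height (%).**

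| σ (cm) | s (cm/yr) | 0-2 y, fixed | 0-2 y, independent | 0-3 y, fixed | 0-3 y, independent |
|---|---|---|---|---|---|
| 0.5 | 0.25 | 93 | 94 | 89 | 93 |
| 0.5 | 0.5 | 89 | 93 | 83 | 91 |
| 0.5 | 1.0 | 86 | 91 | 79 | 88 |
| 0.5 | 1.5 | 84 | 90 | 78 | 87 |
| 1.0 | 0.25 | 94 | 95 | 93 | 95 |
| 1.0 | 0.5 | 93 | 94 | 89 | 93 |
| 1.0 | 1.0 | 89 | 93 | 83 | 91 |
| 1.0 | 1.5 | 87 | 91 | 80 | 89 |

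Year-1 coverage over the same grid is 95-99.9% with fixed deviations.

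**Bone age, σ = 5 months, s = 2/4/6 months/yr, fixed deviations.** Last-visit coverage is 93/90/88% (0-2 y) and 91/85/81% (0-3 y).

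**Joint arm-by-time test, no true difference, nominal 5%, 400,000 draws, fixed deviations.** Height: 5-8% (0-2 y) and 5-10% (0-3 y). Bone age: 5.1-6.4% and 5.4-8.5%.

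**Checks.**
- With s = 0, coverage is 95% at every visit.
- With baseline and one follow-up there is only one pair of visits, so r = 1 and there is no error.
- Simulation with 80 boys, σ = 0.5, s = 1.0, 0-3 y and fixed deviations gave 99.8%, 93.0% and 79.0% at years 1-3 on complete data. With staggered dropout (20%, then 50%) it gave 99.5%, 89.9% and 78.0%.

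**The case against.** The strongest objection is that the SAP never says the random effect is an intercept. A reader might infer that the trial's intervals are wrong; the text shows only that the covariance is unspecified. This stands, and the point is conditional on it.

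A reader might also infer that the protocol expects some boys to grow abnormally slowly. It does not. Section 2 provides that "the medication may be reduced or discontinued, specifically if growth velocity falls below normal", which is a contingency, and section 7a lists excessive slowing as a potential risk. The section 7a remark that slowing is likelier with letrozole is mostly a difference between arm means, which the arm-by-time terms already absorb. The support for unequal rates within an arm is the age range and the mixed diagnoses, and the puberty and bone-age limits narrow that spread. Some spread remains plausible; its size is unknown.

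Third, the lowest coverages need each boy to keep one rate deviation throughout. Independent yearly deviations roughly halve the shortfall at the larger spreads. Direction is not guaranteed either: if differences partly reverse (relative deviations 0, 1, 0.5 at the three visits, s = σ = 0.5), the model variance is 0.625 against true values of 0.75 and 0.5625. Year 1 is then too narrow (92.6%) and the last visit slightly too wide (96.1%). This stands too.

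Finally, the SAP does not list the modelled timepoints or say whether the interaction test is joint. These are missing details, not errors. Nor is year 3 the height endpoint, which section 6m places on average 6-7 years from the start of treatment.

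**Conclusion.** The concern holds conditionally, as a worthwhile and inexpensive improvement. It needs three things: a random intercept with constant residual variance, at least two modelled follow-up visits, and boys who differ in rate of growth or bone-age advance. The first is the natural reading of the SAP, the second fits its wording and the visit schedule, and the third is plausible from the population. None is documented outright.

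Under those conditions the intervals are mis-sized. If spread widens with time they are too wide at year 1 and too narrow at the last visit. The size runs from negligible, when velocity spread is small relative to residual SD, to last-visit height coverage of about 84% (0-2 y) or 78% (0-3 y) at the extreme of the assumed range with fixed deviations, or 90% and 87% with independent ones. The joint interaction test is at most mildly to moderately oversized. All these figures are illustrations; none is an estimate of this trial's actual coverage.

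**What to change.** Name the random-effect structure that was fitted, and the visits in the model. If it already included a richer covariance or robust standard errors, that statement is enough.

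Otherwise, for height and bone age, keep the mean model and fit an unstructured visit covariance with Kenward-Roger or Satterthwaite degrees of freedom. If it does not converge, keep the same mean model and use cluster-robust standard errors with a small-sample correction. Because the SAP is written in the past tense, report this at least as a labelled sensitivity analysis beside the original fit.

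In simulation (fixed deviations, 20 or 40 per arm, 10% random dropout a year), the unstructured fit gave last-visit coverage of 94.4-95.5% and a joint test rejecting 4.7-5.8%. That used an F test with completers minus 2 degrees of freedom as a stand-in; Kenward-Roger itself was not run.

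The cost is a few lines of R and a sentence or two of SAP text, with no new data. The covariance has 6 parameters for three visits or 10 for four, against 2 for a random intercept, so it may not converge in small arms. The documents do not give numbers per arm, and randomisation stopped at the March 2016 renewal. Late intervals would widen: at σ = 0.5, s = 1.0 and fixed deviations, by 1/0.745 ≈ 1.3 at year 2 (0-2 y) or 1/0.635 ≈ 1.6 at year 3 (0-3 y). Year-1 intervals would narrow.
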